## **Sample Size and Population**

We will recruit 104 law enforcement officers (52 at Albuquerque, 26 at Portland, and 26 at Madison). Using a 2:1.5:1 randomization allocation ratio for MBRT, SME, and NIC conditions, respectively, across three sites, 47 participants will be randomized to MBRT; 35 to SME; and 22 to NIC. Participants will be stratified by gender to ensure equivalent gender representation across conditions.

All participants will be invited to participate in individual feedback interviews via phone after the post-course assessment.

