MBRT and SME groups will be led by separate interventionists, with at least masters level training in mental health or a related field, and matched for level of education and experience. MBRT interventionists will have previous training in and experience with MBRT or related interventions (e.g., MBSR, MBCT or MBRP), and will undergo intensive training, weekly clinical supervision, and regular meetings with MPIs to discuss fidelity and other clinical issues. Drs. [name], [name], and [name] are clinical psychologists with combined knowledge of psychoeducational protocols, MBIs, first responder populations, trauma, substance abuse, and other psychosocial outcomes. Given the importance of internal validity of interventions in RCT research, careful attention will be given to intervention adherence and consistency across sites, with all sessions being audio and video recorded. Under the supervision of [name], [name], and consultant [name], advanced graduate students at both study sites will review four randomly selected sessions from each MBRT cohort to assess intervention fidelity, adapting the MBRP Adherence and Competence measure used in previous trials. Drs. [name], [name], and [name], as well as consultant [name], will do the same for each SME cohort. Drs.

[name], [name] and [name] will provide weekly supervision to all interventionists to ensure fidelity and minimize drift. Participants in the NIC condition will not engage in a training; therefore, the administration of this group will only entail scheduling and meeting NIC participants for data collection.

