## 5.2 Handling of Study Interventions

Both the MBRT and SME interventions will follow a session-by-session protocol. They will both be delivered in 8 weekly sessions with a total training time of 17 hours. Both groups include psychoeducation, gentle movement exercises, and weekly homework assignments.

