# 6. STUDY PROCEDURES

## 6.1 Schedule of Evaluations

Assessmen	Phone Screen	Baseline, Enrollment, Randomizat ion: Visit 1	Post-interventi on: Visit 2	3 Month Follow-Up: Visit 3	6 Month Follow-Up: Visit 4
Verbal Consent	X				
Inclusion/Exclusion Criteria	X				
Informed Consent	X				
Alcohol Misuse	X	X	X	X	X
Depression	X	X	X	X	X
Suicidal Ideation	X	X	X	X	X
Trauma Symptoms	X	X	X	X	X
Medication Use		X	X	X	X

Assessment	Phone Screen	Baseline, Enrollment, Randomization: Visit 1	Post-intervention: Visit 2	3 Month Follow-Up: Visit 3	6 Month Follow-Up: Visit 4
Current Psychological Treatment		X	X	X	X
Tobacco Use		X	X	X	X
Adverse Childhood Experiences		X			
C-reactive protein		X	X	X	
IL-6		X	X	X	
IL-10		X	X	X	
TNF- $\alpha$		X	X	X	
Aggression		X	X	X	X
Psychological Resilience		X	X	X	X
Sleep Disturbance		X	X	X	X
Mindfulness		X	X	X	X
Self-Compassion		X	X	X	X
Burnout		X	X	X	X
Sustained Attention to Response Task		X	X	X	X
Interoceptive Awareness		X	X	X	X
Perceived Stress		X	X	X	X
Treatment Expectancy/Credibility (MBRT and SME)		X			
Global Impression of Change (MBRT and SME)			X		
Acceptability (procedures)			X		
Acceptability (MBRT and SME)			X		
Compliance (MBRT and SME)			X		

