### **Randomization**

Immediately following completion of the Zoom-facilitated baseline assessment session, and confirmed completion of the dried blood spot sample, study staff not involved in data collection will randomly assign participants to condition using SPSS and REDCap. The study statistician will create an allocation table using SPSS, and upload it to REDCap, which will be used to implement the randomization procedure for all sites. All trial randomization codes will be stored within REDCap, which is a secure (HIPAA-compliant) internet-based survey and data management software system housed on a secure server at Oregon Health and Science University.

Participants will then be notified via phone of group assignment by a study team member. Participants assigned to MBRT and SME conditions will receive emailed information regarding course structure, dates/times, and class format. All participants will be provided information on assessment timeline, reminder calls they will receive, and contact information for the research team. Initiation of study intervention will be between 1 and 21 days. Participants assigned to SME or NIC will be offered an opportunity to participate in an MBRT course after the final 12-month follow-up collection of departmental excessive use of force data. Participants in all conditions will have access to resources provided by PPB, APD or MPD, including counseling services.

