## 7.3 Adverse Events and Serious Adverse Events

An **adverse event (AE)** is defined as any unfavorable and unintended diagnosis, symptom, sign (including an abnormal laboratory finding), syndrome or disease which either occurs during the study, having been absent at baseline, or if present at baseline, appears to worsen. Adverse events are to be recorded regardless of their relationship to the study intervention.

A **serious adverse event (SAE)** is defined as any untoward medical occurrence that results in death, is life threatening, requires inpatient hospitalization or prolongation of existing hospitalization, results in persistent or significant disability/incapacity, or is a congenital anomaly.

[name] (Portland and Madison) or [name] (Albuquerque) will contact any participant who endorses suicide risk as evidenced by Concise Health Risk Tracking (CHRT) endorsement of suicidal ideation (i.e., Agree or Strongly Agree on one or more “active suicidal ideation or plans” items #10, #11 and/or #12). Drs. [name] or [name] will gather more information and make an appropriate referral for mental health services.

Research staff will be trained to identify potential for risk and adverse events. All student research assistants will be advanced doctoral students in clinical psychology, both of the MPIs ([name] and [name]) and Co-I ([name]) are licensed clinical psychologists. Thus, the research team has an attunement to potential adverse events that will be augmented with training and preparation. Together, the training team will focus on preparing all team members to identify potential risks for adverse events and what steps to take if such risk occurs. Collection of AE's and SAE's will be unsolicited. If an AE or SAE occurs, trained study staff will adhere to the Report Procedures outlined in section 7.4.

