When a participant drops out, we will attempt to obtain information from that LEO regarding the reason for withdrawal. This information will allow us to determine the nature of the missing data (i.e., missing completely at random, missing at random, missing not at random) for analytic purposes; assess whether the withdrawal is due to a protocol violation and if the LEO experienced an AE due to the intervention (if the LEO is in the MBRT or SME arm); and obtain information that could inform future program modifications (e.g., increase the flexibility of program delivery, reduce participant burden, etc.). All protocol violations will be handled by having the Co-PIs meet with relevant study staff to identify the nature of the violation, the reason for the violation, and potential remediations; the Co-PIs will then work with all relevant study staff to implement a remediation plan and decide on a timeframe for re-assessing the procedure to ensure the violation is not re-occurring.

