#### Outcomes (MBRT and SME groups)

- What changes, if any, did you notice in your resilience after completing the training?
- Did the training affect your ability to cope with stress?
- Has the training impacted your day-to-day work?

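### Adverse events are collected unsolicited while MBRT and SME have far more staff contact than NIC, so recorded rates will tend to be higher in the trained arms at equal true rates (suicidal ideation excepted)

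*Combined protocol and SAP*

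**What the plan says.** Section 7.3 defines an AE broadly, records it whether or not it is related to the intervention, and then states: "Collection of AE's and SAE's will be unsolicited". The schedule in 6.1 has no AE row.

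Contact differs by arm. Of MBRT and SME, 5.2 says: "They will both be delivered in 8 weekly sessions with a total training time of 17 hours". Of NIC, section 3 says that "the administration of this group will only entail scheduling and meeting NIC participants for data collection".

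Two smaller routes are also confined to the trained arms. The interview questions on perceived change (9.6) are for MBRT and SME only. The inquiry at withdrawal (9.2) seeks a reason from every participant but also asks "if the LEO experienced an AE due to the intervention (if the LEO is in the MBRT or SME arm").

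Several things are the same in all arms:
- Suicidal ideation is asked at every assessment, and a clinician follows up a positive answer (7.2).
- Depression, trauma symptoms, alcohol misuse, sleep disturbance, perceived stress, medication use and "Current Psychological Treatment" are on the schedule for every arm (6.1).
- On the interview, the Précis says: "All participants will be invited to participate in individual feedback interviews via phone after the post-course assessment".
- On calls and contact details, 6.2.2 says: "All participants will be provided information on assessment timeline, reminder calls they will receive, and contact information for the research team".

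Under 7.4, AEs are graded for severity and relatedness. Under 9.4, the Independent Monitoring Committee (IMC) receives a Closed Safety Report with unmasked safety data by group.

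**The concern.** With no scheduled question, an AE is recorded when an officer volunteers it or trained staff notice it. MBRT and SME participants have eight more occasions for this than NIC participants. Because unrelated events count too, ordinary background illness and injury should occur in every arm but be captured more fully in two of them.

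NIC is the only untreated reference. When the IMC, or a later reader of an AE table by arm, sets MBRT or SME beside NIC, a true difference is mixed with a difference in contact. The distortion runs against the trained arms: equal rates look like mild harm, and a true reduction looks smaller than it is. Relatedness grading does not repair this, since it sorts events already recorded and cannot recover NIC events that nobody heard about.

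The trial is also meant to find procedural flaws before an efficacy trial (9.1), so an AE method left as it is may be carried forward.

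**Working it through.** **The plan's own figures.** Hours from 5.1: MBRT 6 × 1 + 7 + 4 = 17; SME 6 × 1.5 + 4 + 4 = 17. The stated totals reproduce, and the two trained arms match.

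**Model.** Let q be the chance that a lasting AE is mentioned or noticed at one contact. With k contacts after onset, the share recorded is 1 − (1 − q)^k. This rises with k for every q strictly between 0 and 1, so the direction does not depend on the value of q. The size does. The documents give no q, onset pattern or AE rate; q = 0.05, 0.10 and 0.20 are assumptions.

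**Contacts, in weeks.** Sessions at 1 to 8 (trained arms only). In all arms: post-course visit 9.5, interview 10, 3-month visit 8 + 90/7 = 20.9, 6-month visit 8 + 180/7 = 33.7. The 90 and 180 days are from 6.2.4; the exact post-course and interview weeks are assumed.

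**No adjustment, q = 0.10, onset spread evenly over the 8-week course.**
- NIC: k = 4, share 1 − 0.9^4 = 0.344.
- MBRT or SME: k falls from 12 to 5 as onset moves from week 1 to week 8. The mean of 1 − 0.9^k over k = 5 to 12 is (8 − 3.363)/8 = 0.580.
- Ratio 0.580/0.344 = 1.69.

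**No adjustment, q = 0.10, onset spread evenly over 34 weeks.**
- NIC: (9.5 × 0.344 + 0.5 × 0.271 + 10.86 × 0.190 + 12.86 × 0.100)/34 = 6.75/34 = 0.199.
- MBRT or SME: (4.637 + 1.5 × 0.344 + 0.5 × 0.271 + 10.86 × 0.190 + 12.86 × 0.100)/34 = 8.64/34 = 0.254.
- Ratio 1.28.

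**Adjustments that narrow the gap.** Three were tried: three reminder calls in every arm, half a week before each later visit (6.2.2 promises calls but not their number); six of 8 sessions attended, averaged over which six (six is the completer threshold in 5.4); and q halved in group sessions (an assumption; 5.1 gives groups of 10 to 13). With all three and onset in the course, NIC has k = 7, so its share at q = 0.10 is 1 − 0.9^7 = 0.522; the trained-arm share is 0.596; the ratio is 1.14.

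Ratio of recorded rates, MBRT or SME to NIC, at equal true rates:

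| Assumptions | Onset | q = 0.05 | q = 0.10 | q = 0.20 |
|---|---|---|---|---|
| None of the three | any time | 1.37 | 1.28 | 1.16 |
| None of the three | course | 1.88 | 1.69 | 1.41 |
| Calls only | any time | 1.18 | 1.12 | 1.05 |
| Calls only | course | 1.46 | 1.33 | 1.15 |
| Six of 8 sessions only | any time | 1.29 | 1.23 | 1.13 |
| Six of 8 sessions only | course | 1.68 | 1.55 | 1.34 |
| Half chance in sessions only | any time | 1.20 | 1.16 | 1.10 |
| Half chance in sessions only | course | 1.47 | 1.38 | 1.25 |
| All three | any time | 1.07 | 1.05 | 1.03 |
| All three | course | 1.19 | 1.14 | 1.08 |

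**Effect on a true benefit.** A true halving would show as 0.5 × the ratio. For onset in the course that is 0.54 to 0.60 with all three adjustments and about 0.70 to 0.94 with none.

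**The case against.** The strongest reply is that nothing formal rests on this. The trial tests no efficacy hypothesis (9.1) and has no interim analysis (9.4), and the Closed Safety Report supplies group data without a test, ratio or NIC threshold. The IMC knows the design, and the error runs in the cautious direction. All of this stands and limits the importance to a descriptive comparison.

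The main psychological harms are also measured identically in all arms, so worsening can be compared by arm on those scales without contact bias. That stands for the scales. But only suicidal ideation carries an action rule (7.2); nothing turns the other scores, or the medication and treatment answers, into AE records.

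The size is assumed throughout. The model covers lasting AEs only, whereas section 7 names minor aches and mild distress, and it ties every report to a scheduled contact although all arms can telephone the team. This is fair: the table shows how the ratio behaves under stated assumptions and is not an estimate for this trial.

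Unsolicited collection is a deliberate choice for interventions the protocol calls low risk (7.2), with staff trained to spot AEs (7.3). That explains the choice but does not address unequal contact; trained staff see participants mostly in sessions.

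A reader might go further and infer that the trial could be stopped wrongly. The documents do not support that: the safety criterion in 9.4 asks whether the intervention is associated with adverse effects, without an MBRT:NIC ratio, and 7.4 adds relatedness grading.

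**Conclusion.** The concern holds as an avoidable bias in describing AEs against NIC, both in the Closed Safety Report and in any AE table by arm. Apart from suicidal ideation, the expected recorded rate is higher in MBRT and SME than in NIC at equal true rates, provided the chance of mention per contact lies strictly between 0 and 1.

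The size cannot be derived from the documents. For lasting AEs with q from 0.05 to 0.20, the ratio is 1.03 to 1.07 (any time) or 1.08 to 1.19 (course) if all three adjustments apply, and 1.16 to 1.37 or 1.41 to 1.88 if none does.

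Two stronger readings are not supported. One is a doubling of recorded AEs: in this model it needs events already present at the first session, q of 0.10 or less and no adjustment (12 against 4 contacts: 0.718/0.344 = 2.09 at q = 0.10). The other is that the MBRT versus SME comparison is compromised: both have 8 sessions and 17 hours, so it is largely unaffected.

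**What to change.** In 7.3 and 6.1, add one identical question to the post-course, 3-month and 6-month surveys in all three arms: any new or worse physical or emotional problem since the last assessment, when it began, and whether it continues. In 9.2, ask the same question of every participant who withdraws. Route the answers to the clinicians who complete the AE forms (7.4), away from the blinded assessors. Keep unsolicited reporting for safety. In the Closed Safety Report (9.4), compare arms only on the solicited AEs, as n/N with two-sided exact 95% intervals, and list AEs first learned in sessions or interviews separately. If arms answer alike, the expected ratio on solicited AEs is 1.0.

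The cost is one short item in surveys already planned and a few more AE forms to grade; no visit is added. The limits should be stated. Unblinded participants may still answer differently by arm. Intervals stay wide: with zero events the upper limit is 1 − 0.025^(1/n), which is 7.5% for 0 of 47 and 15.4% for 0 of 22. Section 3 describes two cohorts; if the first was already followed without the question it should be shown separately, and NIC shrinks further (if 11 remained, as an assumption, 0 of 11 allows 28.5%). The main gain may therefore be for cohorts still to be followed and for the future efficacy trial.

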## **7.4 Reporting Procedures**

All AEs will be documented using the Adverse Event Form and stored in REDCap. Drs. [name] (Portland and Madison) and [name] (Albuquerque) will be responsible for completing Adverse Event Forms. AEs will be classified by severity level and relatedness to the study. Minimally, the MPI's will be contacted in the event of any AE. The MPI's will review the list of AEs with the Independent Monitoring Committee (IMC) on a semi-annual basis. SAEs that are unanticipated, serious, and possibly related to the study intervention will be reported to the IMC, IRB, and NCCIH in accordance with requirements.

- Unexpected fatal or life-threatening SAEs related to the intervention will be reported to the NCCIH Program Officer within 72 hours. Other serious and unexpected SAEs related to the intervention will be reported to the NCCIH Program Official within 15 days.
- Anticipated or unrelated SAEs will be handled in a less urgent manner but will be reported to the IMC, IRB, NCCIH, and other oversight organizations in accordance with their requirements. In the annual AE summary, the IMC Report will state that they have reviewed all AE reports.

## **7.5 Followup for Adverse Events**

AEs will be tracked by Drs. [name] (Portland and Madison) and [name] (Albuquerque) until resolved or stable. The Adverse Event Forms will be used to document actions taken and outcomes of all AEs.

## **7.6 Safety Monitoring**

Per the NICCIH Program Official ([name]), this study will be monitored by an Independent Monitoring Committee. IMC details are in section 9.4 (Interim Analyses and Stopping Rules)

## **8. INTERVENTION DISCONTINUATION**

If a participant endorses suicidal ideation at any point during the study, they will be referred for psychological treatment and evaluated by Drs. [name] (Portland and Madison) or [name] (Albuquerque) using the CHRT for suitability to continue in the study.

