## 7.2 Methods and Timing for Assessing, Recording, and Analyzing Safety Parameters

The interventions in this study are low risk. Therefore we do not anticipate intervention-related risk to participant safety. In addition to screening, suicidal ideation will also be assessed at baseline, post-intervention, 3- and 6-month follow-up. [name] (Portland and Madison) or [name] (Albuquerque) will contact any participant who endorses suicide risk as evidenced by Concise Health Risk Tracking (CHRT) endorsement of suicidal ideation (i.e., Agree or Strongly Agree on one or more “active suicidal ideation or plans” items #10, #11 and/or #12). Drs. [name] or [name] will gather more information and make an appropriate referral for mental health services.

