### **9.3 Definition of Populations**

Our sensitivity and responsiveness analyses will utilize an ITT approach. If attrition occurs, the study statistician will review the reasons for withdrawal to determine if missing data are missing completely at random (MCAR), missing at random (MAR), or missing not at random (MNAR). If data are MCAR, then we will use a complete-case approach to estimate parameters and conduct sensitivity and responsiveness analyses. If missing data are MAR or MNAR, we will employ a multiple imputation approach to impute data before estimating parameters and conducting sensitivity and responsiveness analyses. We will also estimate parameters and conduct sensitivity and responsiveness analyses using a complete-case approach for comparison purposes.

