## **9.6 Data Analyses**

### Quantitative:

Following best practice guidelines including CONSORT feasibility guidelines and past research, we will measure sensitivity (using a relative efficiency approach) and

responsiveness to change (examining within-group change over time). Relative efficiency analyses will be used to establish that our outcome measures are sensitive to differences between our treatment arm of focus (MBRT) and our other two arms - an active control arm (SME) and a no-treatment control arm (NIC). Therefore, sensitivity analyses will focus on assessing the degree to which outcomes are sensitive to study arms and not whether change is significant. Sensitivity to differences for MBRT compared to SME and NIC will be assessed by examining the relative efficiency of each outcome variable for MBRT versus SME and NIC separately. We will calculate the relative efficiency for MBRT versus SME by conducting one-way, between-subjects Analysis of Covariance (ANCOVA) analyses with MBRT versus SME as the independent variable and each outcome variable at post-training as the dependent variable; we will include study site and gender as covariates. We will also conduct ANOVAs using the same independent and dependent variables to ensure that all inferential tests are conducted and identify any potential Type II Errors among the ANCOVAs. We will then divide the *F*-statistic for each behavioral (BlueTeam/departmental use of force; individual indicators of use of force as well as a composite score of use of force using the individual indicators), physiological (C-RP, IL-6, IL-10, TNF- $\alpha$ ), and self-report (aggression, alcohol misuse, depression, suicidal ideation, trauma symptoms, burnout, and psychological resilience) outcome by the largest *F*-statistic among these analyses, such that the larger the number, the more sensitive that outcome is to the impact of MBRT relative to the active control group.

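### After endorsed suicidal ideation, Section 8 does not separate stopping sessions from leaving the study, so follow-up can be lost depending on an analysed outcome

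*Combined protocol and SAP*

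**What the plan says.** Section 8 (Intervention Discontinuation) contains one rule: "If a participant endorses suicidal ideation at any point during the study, they will be referred for psychological treatment". The officer is then evaluated by a designated investigator "using the CHRT for suitability to continue in the study". The rule applies to any participant. Section 5.1 says that NIC officers receive no intervention but complete the same assessments as the two active arms.

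Sections 7.2 and 7.3 deal with the same event. They define endorsement as agreement with one or more of CHRT items 10, 11 and 12. The investigator contacts the officer and "will gather more information and make an appropriate referral for mental health services". Neither section mentions a decision on continuing. Section 7.2 also sets the schedule: "suicidal ideation will also be assessed at baseline, post-intervention, 3- and 6-month follow-up".

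Section 9.6 lists suicidal ideation among the ranked outcomes: "self-report (aggression, alcohol misuse, depression, suicidal ideation, trauma symptoms, burnout, and psychological resilience) outcome". The between-arm models take "each outcome variable at post-training as the dependent variable".

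Section 9.3 states: "Our sensitivity and responsiveness analyses will utilize an ITT approach". It provides multiple imputation when data are missing at random or not at random, with complete-case results for comparison. Section 6.2.5 has the coordinator ask why an officer discontinued the intervention. It continues contact only after an intervention-related adverse event, until that event resolves. Section 7.5 tracks adverse events "until resolved or stable".

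**The concern.** The heading concerns the intervention, but the decision concerns the study. For an MBRT or SME officer, a finding of unsuitability could mean stopping sessions, stopping assessments, or both. For an NIC officer there are no sessions, so it can only mean leaving the study. The trigger is the value of an analysed outcome, and the instrument named for the evaluation is the one that measures that outcome. Officers with the worst values could therefore be the ones whose later values are missing.

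Three things are at stake. The 3- and 6-month data could lose their upper tail on suicidal ideation and on related scores such as depression and trauma. Six-month retention, a feasibility benchmark in Section 1.1, could fall because of a protocol rule rather than officer choice. The remaining scheduled CHRT checks could end for the officers to whom they matter most. That last point carries weight because Section 7.3 makes adverse-event collection unsolicited, so the scheduled CHRT is the protocol's active check on this risk.

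**Working it through.** **1. What each section settles once an officer is found unsuitable**

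| Section | Stopping sessions | Scheduled assessments afterwards |
|---|---|---|
| 8 | Heading only | Not stated; the decision is about the study |
| 6.2.5 | Reason is asked | Not stated; contact only after an intervention-related adverse event |
| 7.2, 7.3 | Not stated | CHRT schedule given, with no provision for an officer found unsuitable |
| 7.5 | Not stated | Event tracking, not a scheduled CHRT |
| 9.3 | Not stated | Handles missing data, does not require collection |

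No section keeps such an officer in the scheduled visits.

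**2. When an endorsement can arise, and what it can remove**

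- Screening: endorsing items 10, 11 or 12 excludes the officer (Section 6.2.1).
- Baseline: assessed before randomization (Sections 4.3 and 6.2.2), so a decision made then is not a loss after randomization.
- Between randomization and the post visit: no scheduled CHRT. Loss would follow an unscheduled disclosure, or a baseline flag acted on late. Only this route reaches the post-training F-ratios and the baseline-to-post responsiveness measures.
- Post visit: the post CHRT value is already recorded. The 3- and 6-month visits could be lost.
- 3 months: the 6-month visit could be lost.
- 6 months: this is the last visit, so nothing scheduled with the officer remains.

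**3. Retention**

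Inputs: N = 47 + 35 + 22 = 104 (Section 3); retention of at least 80% at 6 months (Section 1.1); predicted overall attrition of 20% (Section 9.2).

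- 0.80 × 104 = 83.2, so 84 officers must be retained and at most 104 − 84 = 20 may be lost.
- Predicted attrition is 0.20 × 104 = 20.8, so the plan already expects to be at the limit.
- Each removal costs 1/104 = 0.96 points. A 21st loss gives 83/104 = 79.8%.

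**4. Illustration of the effect on means and SDs**

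The documents give no rate of endorsement or removal, so the fraction q of worst values left unobserved is assumed. For a standard normal outcome cut above c = Φ⁻¹(1 − q), with λ = φ(c)/(1 − q), the mean shifts by −λ and the SD becomes √(1 − cλ − λ²). For q = 5%: c = 1.645, λ = 0.109, SD = √(1 − 0.179 − 0.012) = 0.90. The skewed case is a standardised gamma distribution with shape 0.5, by simulation.

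| q (about n of 104) | Normal: mean shift, SD ratio | Skewed: mean shift, SD ratio |
|---|---|---|
| 1% (1) | −0.03, 0.97 | −0.05, 0.84 |
| 2% (2) | −0.05, 0.95 | −0.09, 0.77 |
| 5% (5) | −0.11, 0.90 | −0.17, 0.62 |
| 10% (10) | −0.20, 0.84 | −0.27, 0.48 |

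Mean shifts are in units of the true SD. These rows assume that removal takes exactly the worst values and that nothing is imputed, so they show direction and scale and are not a forecast.

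**The case against.** The strongest reply is that the planned analyses are hardly touched. Section 9.6 uses post-training values and baseline-to-post change, and specifies no 3- or 6-month outcome model. An endorsement at the post visit or later cannot alter the ranked post CHRT value. This stands, and it limits the point to follow-up data, retention and safety description.

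Several stronger readings are tempting but not supported:

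- A reader might infer that endorsement removes an officer automatically. Section 8 requires an evaluation, so removal is possible and not certain.
- A reader might infer that the officer's risk is no longer followed at all. Referral is required, the investigator makes contact, and a new or worsened symptom can meet the adverse-event definition in Section 7.3 and be tracked under Section 7.5. What may be lost is the scheduled CHRT.
- A reader might infer a contradiction with intention to treat. Section 9.3 pairs that approach with imputation, and a removal driven by a recorded CHRT value could be handled if that value is in the model. However, Section 9.3 specifies no imputation model, and the complete-case comparison would still carry the loss.
- A reader might infer that Section 8 uses a lower threshold than Section 7.2. Its wording widens the time at which endorsement counts and not the level. The natural reading is the items 10–12 definition, although Section 8 does not refer to it.
- A reader might measure one NIC loss as 1/22 = 4.5 points. The benchmark is study-wide, so the cost is about 1 point.

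**Conclusion.** The point holds in a limited form. As written, Section 8 can end study participation because of an endorsement on an analysed outcome, in all three arms, and no section says which assessments continue. The exposure is to 3- and 6-month data, the remaining scheduled CHRT checks and study-wide retention. Retention loses about 1 point per removal, with no slack if the predicted 20% attrition occurs. This assumes that a removed officer counts as lost and would otherwise have been retained. Post-training F-ratios and baseline-to-post responsiveness are affected only by departures between randomization and the post visit. How often officers would be removed cannot be judged from the documents. Screening excludes those who endorse items 10–12 at entry, so numbers may be small. The ambiguity should be resolved because the repair is cheap and the trial is meant to supply means, variability and retention for the next one.

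**What to change.** Reconcile Section 8 with its heading and with Sections 6.2.5, 7.2, 7.3 and 9.3. The revised text should:

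1. State separately what is decided about MBRT or SME sessions and what is decided about study assessments, and say what the rule means for NIC officers.
2. State which already scheduled data (CHRT, other self-report, departmental records) are still collected from consenting officers after a decision to discontinue. Departmental records need no contact with the officer.
3. State that these officers are analysed as randomized.
4. Refer Section 8 to the items 10–12 definition in Sections 7.2 and 7.3, or say that it differs.

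The clinical criterion and the decision on an officer's continued participation stay with the investigators. The cost is a few sentences in Sections 8 and 6.2.5 with matching cross-references. The small downside is that a few officers under referral may still be contacted for scheduled assessments, which remain voluntary.
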